2.0 Data Analysis Considerations

2.1 Types of Analyses

The term summary statistics for quantitative data refers to the following list of statistics unless otherwise specified: n (number of non-missing observations), mean, standard deviation, minimum, median, and maximum. Categorical variables will be summarized with frequency counts and percentage of the relevant group. Summary statistics will be summarized by treatment sequence and study period. Unless otherwise stated, all hypotheses will be tested at a two-sided $\alpha = 0.05$ significance level

2.2 Analysis Populations

The following analysis populations will be defined for the analysis:

- **Safety Population:** All randomized patients who have received at least one dose of study medication.
- **Full Analysis Set (FAS):** The FAS consists of all randomized patients who receive at least one dose of study medication and have at least one post-treatment efficacy assessment.
- **Per Protocol (PP):** The PP population will include all patients in the FAS who have no major protocol deviations.

Exclusion from the FAS and PP populations will be finalized prior to database lock and subsequent unblinding. Data listings will be created to list the subjects excluded from each population, along with the reasons for exclusion.

2.2.1 Subgroup Definitions

Patients will be categorized and grouped for analysis by:

- Genetic deficiencies and mechanistic localization (See Table 2.2-1 below);
- Whether their mutation is pre- or post- synaptic (See Table 2.2-1 below);
- Whether they are an adult (age ≥ 17 years) or pediatric (age < 17 years);
- Pediatric subject ages will be further broken down into categories (2 to less than 6, 7 to less than 12, and 12 to less than 17 years of age).

Table 2.2-1 Genetic Mutation Type and Neuromuscular Junction Localization Type

Mutation	Description	Localization
CHRNE	Codes for the epsilon subunit of the acetylcholine receptor.	Post-synaptic
SNAP 25B	One of the proteins in the SNARE complex responsible for acetylcholine vesicle fusion in presynaptic neurons.	Pre-synaptic
RAPSYN	Anchors and clusters acetylcholine receptors.	Post-synaptic
DOK7	Docking Protein 7: Activates the MuSK protein and catalyzes the development of Neuromuscular Junctions (NMJs) on the muscle.	Post-synaptic
AGRN	Agrin protein secreted by pre-synaptic motor neurons to start and maintain the formation of a NMJ.	Pre-synaptic
CHAT	Codes for choline acetyltransferase that synthesizes acetylcholine in the presynaptic nerve terminal.	Pre-synaptic

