4.1.2 Description of Secondary Efficacy Variables

The following variables will be secondary measures of efficacy:

- Motor Function Measure 20 (MFM-20, for Pediatric Subjects under 7 years) or Motor Function Measure 32 (MFM-32, for all other subjects). MFM-20 or MFM-32 Scores, depending on age, will be calculated as Totals for all items. MFM-20 and MFM-32 dimension scores are totals for item group D1 (Standing and Transfer), item group D2 (Axial and Proximal Motor Function), and item group D3 (Distal Motor Function). Additionally, these Motor Function Measure outcomes are also expressed as a percentage of the respective maximum possible total for all items and the three dimension groups, for both the MFM 20 and MFM 32. The percentages "normalize" the response between MFM 20 and MFM 32 so that

outcomes from these two groups of test subjects can be pooled for analysis across age groups;

- Clinical Global Impression-Severity;
- Clinical Global Impression-Improvement;
- Stimulated Single Fiber Electromyogram: mean jitter, median jitter, and percent block (this optional test is described in the protocol but not conducted at all trial sites);
- Slurp Test: Time (seconds) to make slurp sound (this optional test is described in the protocol but not conducted at all trial sites).

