4.2 Analysis of Efficacy

4.2.1 Analysis of Primary Efficacy

Summary statistics for the SGI Day 0 assessment (baseline for period 1), SGI Day 8 assessment, and the corresponding change from baseline (CFB₁) will be presented by treatment and by treatment within mutation type (pre- vs. post-synaptic, see Table 2.2-1 above) as period 1. A Mann-Whitney-Wilcoxon test for equality of the CFB₁ in the two treatments in Period 1 will be presented. Summary statistics for the SGI Day 21 assessment (baseline for period 2), SGI Day 29 assessment, and the corresponding change from baseline (CFB₂) will also be presented by treatment and treatment within mutation type as period 2. Also, the change in CFB from Period 1 to Period 2 will be computed. This value estimates

$$\tau_1 - \tau_2$$

where τ_1 represents the treatment effect of the period 1 Investigational Product (IP) and τ_2 represents the treatment effect of period 2 IP. A Mann-Whitney-Wilcoxon test of the hypothesis that the above parameter is the same in both treatment sequences will be provided. Note that this is a nonparametric version of the treatment main effect in a linear model without carryover effects.

A mixed effects linear model will be fit to the data with SGI raw scores as the response. The model will include fixed effect terms for treatment, period, age group (2 to less than 6, 7 to less than 12, and 12 to less than 17 years of age, 17 years and over), mutation type and sequence*period, where sequence corresponds to the order in which the subject received treatments, and a random effect for subject. The LSMeans for the treatment groups will be calculated and provided, as will the estimated difference along with a 95% confidence interval for this difference and a formal hypothesis test that the difference in the means is 0.

Special care must be taken in crossover designs to ensure that there is not significant carryover effect; however, the pharmacological properties of amifampridine are such that

having a 12-day washout period should minimize any unequal carryover effects in the analysis.

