A mixed effects linear model will be fit to each of the MFM datasets described above with percent outcome or individual item scores (as appropriate for each dataset) as the response variable. The model will include fixed effect terms for treatment, period, age group (2 to less than 6 years, 7 to less than 12 years, 12 to less than 17 years of age, and 17 years of age and above), genetic mutation type (see Table 2.2-1), and sequence*period, where sequence corresponds to the order in which the subject received treatments, and a random effect for subject. No carryover term will be fit. In the case of the MFM percent outcome datasets for the adult only patients, the age group fixed effect term will not be included in the model. The LSMeans for the treatment groups will be calculated and provided, as will the estimated difference along with a 95% confidence interval for this difference and a formal hypothesis test that difference in the means is 0. Note that it is highly likely that some specific mutations will have insufficient subjects to fit the specified model. In that case a notation will be made in the relevant table(s) that there are not sufficient observations to fit the model.

Special care must be taken in crossover designs to ensure that there is no significant carryover effect; however, the pharmacological properties of amifampridine (an elimination half-life of 1.8-2.5 hours) are such that having a 12-day restabilization period will minimize any unequal carryover effects in the analysis.

Clinical Global Impression

CGI-S and CGI-I will be summarized by frequency tables and percentages for each sequence group and period. The values will be analyzed with a Wilcoxon rank-sum test as outlined in Putt and Chinchilli (2004). The treatment effects will be estimated using the Hodges-Lehmann estimator and a 90% asymptotic confidence interval.

Single Fiber Electromyogram

Summary statistics for mean jitter, median jitter, and percent block will be presented by treatment and visit. No formal inferential procedures will be performed for these data.

Slurp Test

Summary statistics for the time to slurp sound from the slurp test and its CFB (Day 0 for Period 1 and Day 21 for Period 2) will be presented. No formal inferential procedures will be performed for these data.

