7.0 List of Analysis Tables, Figures and Listings

Table No.	Table Title	Included in Tables	Shown in Appendix B
1	Subject Disposition	X	X
2	Baseline Disease Characteristics by Age Group (Safety Population)	X	X
3	Demographics and Baseline Data Summary Statistics – Continuous Variables (Safety Population)	X	X
4	Demographics and Baseline Data Summary Statistics – Categorical Variables (Safety Population)	X	X
5	SGI Score Summary Statistics by Treatment, Period and Time Point (FAS Population)	X	X
6	SGI Score Summary Statistics by Treatment, Period and Time Point (PP Population)	X	
7	SGI Score Summary Mann-Whitney Main Effects Test Results (FAS Population)	X	X
8	SGI Score Summary Mann-Whitney Main Effects Test Results (PP Population)	X	
9	SGI Score Mixed Model Analysis (FAS Population)	X	X
10	SGI Score Mixed Model Analysis (PP Population)	X	
11	MFM-32 Score Summary Statistics by Treatment, Period and Time Point (FAS Population)	X	X
12	MFM-32 Score Summary Statistics by Treatment, Period and Time Point (PP Population)	X	
13	MFM-32 Score Summary Mann-Whitney Main Effects Test Results (FAS Population)	X	X
14	MFM-32 Score Summary Mann-Whitney Main Effects Test Results (PP Population)	X	
15	MFM-32 Score Mixed Model Analysis (FAS Population)	X	X
16	MFM-32 Score Mixed Model Analysis (PP Population)	X	
17	MFM-32 Percent Mixed Model Analysis (FAS Population)	X	X
18	MFM-32 Percent Mixed Model Analysis (PP Population)	X	
19	MFM-20 Score Summary Statistics by Treatment, Period and Time Point (FAS Population)	X	X
20	MFM-20 Score Summary Statistics by Treatment, Period and Time Point (PP Population)	X	
21	MFM-20 Score Summary Mann-Whitney Main Effects Test Results (FAS Population)	X	X
22	MFM-20 Score Summary Mann-Whitney Main Effects Test Results (PP Population)	X	
23	MFM-20 Score Mixed Model Analysis (FAS Population)	X	X
24	MFM-20 Score Mixed Model Analysis (PP Population)	X	
25	MFM-32 Score Mixed Model Analysis by Age Group (FAS Population)	X	X
26	MFM-32 Score Mixed Model Analysis by Age Group (PP Population)	X	

Table No.	Table Title	Included in Tables	Shown in Appendix B
27	MFM Percent-of-Possible Score Mixed Model Analysis (FAS Population)	X	X
28	MFM Percent-of-Possible Score Mixed Model Analysis (PP Population)	X	
29	MFM Percent-of-Possible Score Mixed Model Analysis by Age Group (FAS Population)	X	X
30	MFM Percent-of-Possible Score Mixed Model Analysis by Age Group (PP Population)	X	

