Appendix B – Table, Listing, and Figure Shells

Table 1. Subject Disposition
Catalyst Pharmaceuticals, Inc. - CMS-001

	Amifampridine/ Placebo (N = xx)	Placebo/ Amifampridine (N = xx)	Overall (N = xx)
Screen Failures			xx
Enrolled	xx	xx	xx
Pre-Synaptic	xx (xxx%)	xx (xxx%)	xx (xxx%)
Post-Synaptic	xx (xxx%)	xx (xxx%)	xx (xxx%)
Completed	xx (xxx%)	xx (xxx%)	xx (xxx%)
Pre-Synaptic	xx (xxx%)	xx (xxx%)	xx (xxx%)
Post-Synaptic	xx (xxx%)	xx (xxx%)	xx (xxx%)
Withdrawn	xx (xxx%)	xx (xxx%)	xx (xxx%)
Pre-Synaptic	xx (xxx%)	xx (xxx%)	xx (xxx%)
Post-Synaptic	xx (xxx%)	xx (xxx%)	xx (xxx%)
Reason for Withdrawal	xx (xxx%)	xx (xxx%)	xx (xxx%)
Adverse Event	xx (xxx%)	xx (xxx%)	xx (xxx%)
Pre-Synaptic	xx (xxx%)	xx (xxx%)	xx (xxx%)
Post-Synaptic	xx (xxx%)	xx (xxx%)	xx (xxx%)
Lost To Follow-Up	xx (xxx%)	xx (xxx%)	xx (xxx%)
Pre-Synaptic	xx (xxx%)	xx (xxx%)	xx (xxx%)
Post-Synaptic	xx (xxx%)	xx (xxx%)	xx (xxx%)
Physician Decision	xx (xxx%)	xx (xxx%)	xx (xxx%)
Pre-Synaptic	xx (xxx%)	xx (xxx%)	xx (xxx%)
Post-Synaptic	xx (xxx%)	xx (xxx%)	xx (xxx%)
Withdrawal by Subject	xx (xxx%)	xx (xxx%)	xx (xxx%)
Pre-Synaptic	xx (xxx%)	xx (xxx%)	xx (xxx%)
Post-Synaptic	xx (xxx%)	xx (xxx%)	xx (xxx%)
Other	xx (xxx%)	xx (xxx%)	xx (xxx%)
Pre-Synaptic	xx (xxx%)	xx (xxx%)	xx (xxx%)
Post-Synaptic	xx (xxx%)	xx (xxx%)	xx (xxx%)

The denominator for all percentages in the table is the number of enrolled patients in the pertinent treatment/dose group and overall.
STATKING Clinical Services (yyyy-mm-dd)
Source Program: xxxxxxx.sas

Table 2. Baseline Disease Characteristics by Age Group
Catalyst Pharmaceuticals, Inc. - CMS-001
Safety Population (N=xxxx)

Age Group	Mutation Type		
	Pre-Synaptic (N=xxx)	Post-Synaptic (N=xxx)	Overall (N=xxx)
Adult (>17 years)	xxx (xxx%)	xxx (xxx%)	xxx (xxx%)
Pediatric	xxx (xxx%)	xxx (xxx%)	xxx (xxx%)
2- <7 years old	xxx (xxx%)	xxx (xxx%)	xxx (xxx%)
7- <13 years old	xxx (xxx%)	xxx (xxx%)	xxx (xxx%)
13- <17 years old	xxx (xxx%)	xxx (xxx%)	xxx (xxx%)

STATKING Clinical Services (yyyy-mm-dd)
Source Program: xxxxxxx.sas

Page x of y

Table 3. Demographics and Baseline Data Summary Statistics - Continuous Variables
 Catalyst Pharmaceuticals, Inc. - CMS-001
 Safety Population (N=xxxx)

Variable	Treatment and Mutation Type	Mean	Std Dev	n	Min	Max	Median
Age (years)	Amifampridine/Placebo	xxx	xxx	xxx	xxx	xxx	xxx
	Pre-Synaptic	xxx	xxx	xxx	xxx	xxx	xxx
	Post-Synaptic	xxx	xxx	xxx	xxx	xxx	xxx
	Placebo/Amifampridine	xxx	xxx	xxx	xxx	xxx	xxx
	Pre-Synaptic	xxx	xxx	xxx	xxx	xxx	xxx

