	Least Squares (LS) Mean of Change from Baseline	xxx	xxx
	Between-Treatment Difference in LS Means (A-B)	xxx	
	Denominator degrees of freedom	x	
	95% CI for Between-Treatment Difference in LS Means (A-B)	(xxx, xxx)	
Item xx	n	xxx	xxx
	Least Squares (LS) Mean of Change from Baseline	xxx	xxx
	Between-Treatment Difference in LS Means (A-B)	xxx	
	Denominator degrees of freedom	x	
	95% CI for Between-Treatment Difference in LS Means (A-B)	(xxx, xxx)	

^a Raw MFM score was modeled as the response, with fixed effects terms for treatment, period, age group, mutation type and sequence*period (i.e., carryover). Subject was treated as a random effect.

STATKING Clinical Services (yyyy-mm-dd)

Source Program: xxxxxxxx.sas

Table format repeats for PP population. Individual items will be ordered in increasing order of the p-values for the Crossover test.

Table 17. MFM-20 Score Mixed Model Analysis
 Catalyst Pharmaceuticals, Inc. - CMS-001
 FAS Population (N=xxxx)

Variable	Statistic ^a	Amifampridine/ Placebo	Placebo/ Amifampridine
Overall	n	xxx	xxx
	Least Squares (LS) Mean of Change from Baseline	xxx	xxx
	Between-Treatment Difference in LS Means (A-B)	xxx	
	Denominator degrees of freedom	x	
	95% CI for Between-Treatment Difference in LS Means (A-B)	(xxx, xxx)	
D1 Domain	n	xxx	xxx
	Least Squares (LS) Mean of Change from Baseline	xxx	xxx
	Between-Treatment Difference in LS Means (A-B)	xxx	
	Denominator degrees of freedom	x	
	95% CI for Between-Treatment Difference in LS Means (A-B)	(xxx, xxx)	
D2 Domain	n	xxx	xxx
	Least Squares (LS) Mean of Change from Baseline	xxx	xxx
	Between-Treatment Difference in LS Means (A-B)	xxx	
	Denominator degrees of freedom	x	
	95% CI for Between-Treatment Difference in LS Means (A-B)	(xxx, xxx)	
D3 Domain	n	xxx	xxx
	Least Squares (LS) Mean of Change from Baseline	xxx	xxx
	Between-Treatment Difference in LS Means (A-B)	xxx	
	Denominator degrees of freedom	x	
	95% CI for Between-Treatment Difference in LS Means (A-B)	(xxx, xxx)	
Item xx	n	xxx	xxx
	Least Squares (LS) Mean of Change from Baseline	xxx	xxx
	Between-Treatment Difference in LS Means (A-B)	xxx	
	Denominator degrees of freedom	x	
	95% CI for Between-Treatment Difference in LS Means (A-B)	(xxx, xxx)	

^a Raw MFM score was modeled as the response, with fixed effects terms for treatment, period, age group, mutation type and sequence*period (i.e., carryover). Subject was treated as a random effect.

STATKING Clinical Services (yyyy-mm-dd)

Source Program: xxxxxxxx.sas

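### The SAP's age bands leave patients aged 6 to under 7 without a level in the SGI and MFM mixed models, and the table shells use conflicting bands

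*SAP*

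**What the plan says.** **Age.** SAP 2.2.1 sets paediatric "categories (2 to less than 6, 7 to less than 12, and 12 to less than 17 years of age", with adults from 17. The SGI mixed model in 4.2.1 has a fixed effect for "age group (2 to less than 6, 7 to less than 12, and 12 to less than 17 years of age" plus 17 and over. The MFM mixed models in 4.2.2 have one for "age group (2 to less than 6 years, 7 to less than 12 years, 12 to less than 17 years of age" plus 17 and over. SAP 4.1.2 splits the motor function forms at a different age: "MFM-20, for Pediatric Subjects under 7 years". Protocol inclusion criterion 2 admits patients from age 2 with no upper limit.

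**Shells (SAP Appendix B).** Table 2 has 2-<7, "7- <13 years old" and 13-<17. Table 4 has 2-<7, 7-<12 and 13-<17. Table 25 (MFM-32 only) has 7-<12 and 13-<17. The Table 31 footnote describes MFM-20 patients as 2 to <7.

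**Mutation.** SAP Table 2.2-1 has rows for CHRNE, SNAP 25B, RAPSYN, DOK7, AGRN and CHAT. It is the SAP's only key to mutation and to pre- or post-synaptic class, and both models use it. Inclusion criterion 4 names seven subtypes, including MuSK, SYT2 and fast channel syndrome.

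**Age term.** SAP 4.2.2 makes one exception: "for the adult only patients, the age group fixed effect term will not be included in the model". The footnotes of Tables 9 and 15 include age group. Those of Tables 23, 27, 29 and 31 leave it out.

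**Title.** SAP 7.0 lists Table 17 as "MFM-32 Percent Mixed Model Analysis (FAS Population"; its shell is headed "Table 17. MFM-20 Score Mixed Model Analysis".

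**The concern.** A fixed effect needs a level for every analysed patient. A patient aged 6 to under 7 has none under the wording of the model sections. If the bands are programmed as written, the derived age group is blank and the patient leaves the fit. Otherwise someone chooses a band that the SAP does not authorise.

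For SGI this touches the only planned confidence interval. The mixed model gives the treatment difference with a 95% interval, while the Table 7 shell for the rank tests shows a mean difference, a test statistic and a p-value. A 12-year-old would also belong to no stratum of Table 25.

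The mutation key raises the same question on weaker ground: a MuSK or SYT2 patient has no class for the models or for the summaries by mutation type.

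**Working it through.** The plan gives no figure of its own on this point. The check is one of coverage.

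**1. Age bands.** Each whole year of age from 2 up, tested against each set of bands:

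| Source | Paediatric bands | Uncovered age | Share of age range |
|---|---|---|---|
| SAP 2.2.1, 4.2.1, 4.2.2 | 2-<6, 7-<12, 12-<17 | 6 | 1 of 15 years (2-16); 1 of 5 MFM-20 years (2-6) |
| Table 2 | 2-<7, 7-<13, 13-<17 | none | 0 |
| Table 4 | 2-<7, 7-<12, 13-<17 | 12 | 1 of 15 years |
| Table 25 (ages 7 and over) | 7-<12, 13-<17 | 12 | 1 of 10 years (7-16) |
| Proposed | 2-<7, 7-<12, 12-<17 | none | 0 |

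These are shares of the age range, not of patients.

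**2. What one lost patient would weigh.** SAP 1.1 plans up to 23 patients and SAP 1.3 speaks of 23 per sequence. One patient is 1/23 = 4.3% of the first figure, or 1/(2 × 23) = 2.2% of the second.

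**3. Where the gap bites.** For SGI, 4.2.1 and the Table 9 footnote both include age group, so the gap applies whichever is followed. For MFM, a 6-year-old is assessed with the MFM-20. The footnotes of Tables 23, 27, 29 and 31 omit age, so the patient stays in if the footnote is followed and drops out if 4.2.2 is followed.

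**4. Mutation key.** Of the seven subtypes in criterion 4:
- three match a row directly (Rapsyn, Dok-7, SNAP25B);
- one matches loosely (acetylcholine receptor defect to CHRNE, which is the epsilon subunit only);
- two have no row (MuSK, SYT2);
- one is not placed (fast channel syndrome).

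That accounts for 3 + 1 + 2 + 1 = 7. AGRN and CHAT have rows but are not named in criterion 4.

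**5. Does omitting the age term matter?** Let patient *i* in age group *g* have, in period *p*, the response y(i,p) = μ + a(g) + π(p) + τ(treatment) + b(i) + e(i,p). The within-patient difference is

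y(i,1) − y(i,2) = [π(1) − π(2)] + [τ(first treatment) − τ(second treatment)] + [e(i,1) − e(i,2)].

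The age effect a(g) cancels. The patient's total carries no information on treatment, because every completer receives both treatments. The age term therefore leaves the treatment difference unchanged for patients who complete both periods. The model's sequence*period term raises a separate question and is set aside here.

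With the first cut at 7, the age factor has 4 levels for Table 27, 3 for Table 29 part 1, and 1 for the MFM-20-only Table 23, where leaving it out is harmless.

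**The case against.** The strongest reply is that this is a slip whose correction is visible. Shells 2 and 4, the form split in 4.1.2 and the Table 31 footnote all point to 2 to <7. A 6-year-old's age is observed, so the complete-case rule in SAP 2.3 does not itself remove the patient, and a blinded programmer would query the gap. The intention is indeed fairly clear. But the cut at 6 appears in all three defining sections, two of them model specifications, and the shells disagree among themselves about age 12. The SAP should not leave the choice to the programmer.

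On mutation, parts of the SAP are in the past tense, and its table contains AGRN and CHAT, which criterion 4 does not name. That fits a list of mutations actually enrolled, in which case nobody lacks a level. Each patient's mutation is also recorded in the listings. The SAP does not say the table is such a list, so the gap stands on paper only.

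A reader might infer that omitting age from the footnotes biases the treatment effect. It does not for completers (step 5), and adding age to the small single-mutation fits of Table 31 could make them fail. SAP 4.2.2 already expects some mutations to have too few patients to fit the model.

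**Conclusion.** The age-band point holds. As written, the SAP gives an eligible patient aged 6 to under 7 no level in the SGI and MFM mixed models, and shells 4 and 25 do the same to 12-year-olds. The size is one uncovered year of age in each band set concerned. How many patients that means is not in the documents and may be zero.

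A reader might go further and infer that patients were lost or that the efficacy conclusion is compromised. The documents do not support that. They do not show that anyone of the uncovered ages was randomised, and the all-patient Mann-Whitney-Wilcoxon tests use neither age nor mutation. Loss from the mixed models also assumes literal programming of the bands.

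The mutation key is a secondary point of the same kind, with a plausible innocent explanation. The age-term footnotes and the Table 17 title are housekeeping.

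**What to change.** Before unblinding:

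1. Use 2 to <7, 7 to <12, 12 to <17, and 17 and over in SAP 2.2.1, 4.2.1 and 4.2.2 and in shells 2, 4 and 25 (Table 25 from age 7). The first cut then matches the MFM-20/MFM-32 split.
2. Either give every criterion 4 subtype a mutation level and a pre- or post-synaptic class in Table 2.2-1, or state that the table lists only enrolled mutations. In the same edit, reconcile the AGRN and CHAT rows with criterion 4.
3. Housekeeping, after step 1: align the age term in the footnotes of Tables 27 and 29 (part 1) with 4.2.2. If this were done before the bands are repaired, the gap would enter those tables too. Do not add the age term to the single-mutation fits of Table 31; record that exception in 4.2.2. Leave Table 23 without it. Correct the Table 17 shell title.

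The cost is wording in three SAP sections, one table and a few shells and footnotes. No new data or analyses are needed.

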2.3 Missing Data Conventions

All analyses will be based on the observed data without imputation, i.e., a complete case analysis.

2.4 Interim Analyses

No unblinded interim analyses of the data were conducted.

2.5 Study Center Considerations

Although CMS-001 is a multi-center study, data from all sites will be pooled for this analysis. No provision is made for selective pooling of study sites.

